Several methodological considerations will allow for a more accurate account of the patterns of functional activation for the participants with aphasia. First, an event-related study design will be used in which brain responses to correctly and incorrectly named items can be distinguished and compared across time-points [26]. Secondly, measurements of hemodynamic response (HRF), which are used to estimate the neural response related to the naming event, will be calculated for each individual participant. This is important because individuals with aphasia are known to have delayed HRF or HRF that is decreased in amplitude, resulting in erroneous or underestimated measures of brain activity when canonical HRF estimates are used [43]. Third, dynamic (activity-dependent), directional coupling, known as effective connectivity, will be estimated for regions in the RH and LH to measure interactivity changes across time resulting from rTMS.

C.1 Procedures:

The schedule of study procedures across the 13 study sessions is summarized in Figure 4. During the initial session, enrolled participants will be assessed with the Philadelphia Naming Test (PNT; [44]) and the Comprehensive Aphasia Test (CAT; [45]). In cases where apraxia of speech is suspected, the Apraxia Battery for Adults (ABA-2; [46]) may be administered in whole or in part. Participants may also be assessed with other psycholinguistic and naming measures. The first session will conclude with the baseline MRI scan (described in detail below). If, following the screening session, a participant is found to be eligible they will be scheduled for all remaining study-related visits.

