Motor Threshold and Intensity Determination. To standardize TMS stimulation intensity prior to rTMS, a resting motor evoked threshold (MT) will be established based on a distal upper extremity motor response. The MT will be measured by delivering single stimulations to the motor cortex with gradually increasing intensity no more frequently than every 3 sec, i.e. ~0.3 Hertz. Threshold is defined as the lowest intensity of stimulation producing motor evoked potentials of at least 50 μ V (or a visible movement of the digit) in 5 of 10 trials. Our standard stimulation intensity will be 90% of the MT.

Individual fMRI-based coil targeting. Evidence suggests that the degree of spatial resolution required to target specific cortical sites such as the PTr is achieved more readily when rTMS is used in conjunction with image-guided navigation techniques [48]. This stereotactic targeting also ensures more consistent coil placement across sessions. Following individual determination of stimulation intensity, coil placement individually targeted to the RH PTr will be performed using a frameless stereotactic method as described in Neggers and colleagues [49] and will be implemented in the BrainVoyagerQX software neuro-navigation package. Following coil positioning, participants will receive rTMS treatment according to their group assignment (see below).

TMS Administration.

Group A: Inhibitory only rTMS group: Inhibitory 1Hz rTMS will be applied continuously for 1200 pulses (20 minutes) 5 days per week across 2 weeks (10 sessions total).

Group B: Excitatory primed rTMS group: The inhibitory sequence described above will be preceded for each session by priming stimulation which will consist of intermittent 6-Hz rTMS applied in 5 second trains with 25 second intervals between trains for a total 600 pulses (10 minutes).

C2. Data Analysis

C2.1 Analysis of Behavioral Measures: Naming data (item-level performance on the PNT) will be used for analysis of rTMS treatment effects by group. Accuracy data will be analyzed using multilevel linear or logistic regression in R. Models will include fixed effects of session (baseline, post-treatment, follow-up), and group (Group A, Group B) and random effects of subject and item. Analyses may include additional random-effects structure if needed to improve model fit.

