Dynamic causal modeling (DCM) will be used to estimate effective connectivity changes due to inhibitory rTMS across time. Regions to be included in the DCM analysis will be derived from clusters of contiguous voxels surviving an omnibus F-test for the effect of interest (correct naming > crosshair fixation) at $p < 0.001$ uncorrected from the first-level fMRI analysis. Regions will be constrained to only include those clusters that fall within the traditionally outlined “language network” in the LH (inferior frontal lobe, temporal lobe, and portions of the inferior and posterior parietal lobe, [51]) and the corresponding RH homologues. The effective connectivity model (estimate of coupling and weights between these regions) will be estimated via post-hoc network discovery methods [52]. This method uses Bayesian model selection methods to select the model that was the most likely to have generated the time series data from all possible combinations of bi-directional connections between the regions. Coupling weights for interhemispheric connections will be summed for each participant for each scanning session. Other post-hoc analyses of the DCM results may be undertaken to explore both inter- and intra-hemispheric network level effects of the rTMS.

Finally, change in naming accuracy on the PNT across sessions will be correlated with change in LI, functional activation in RH PTr, and interhemispheric effective connectivity across sessions. A positive correlation between naming gains and 1) a left-hemisphere directed LI shift, and 2) a decrease in RH inhibition of LH (more positive RH to LH directional coupling weights) will support Hypothesis 1a and 1b, respectively. A positive correlation between the magnitude of pre-TMS RH PTr activation and 1) decrease in RH PTr activation across scan sessions, and 2) magnitude of left-hemisphere directed LI shift will support Hypothesis 2a and 2b, respectively. A significant interaction of group and session (analysis C2.1) suggesting that Group B receiving the 6 Hz primed inhibitory rTMS showed greater naming improvement across time will support Hypothesis 3.

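### Hypotheses 1a, 1b, 2a and 2b are judged by the sign of a correlation alone, with no significance level or fixed change interval, and for 2a regression to the mean favours the predicted sign

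*Combined protocol and SAP*

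**What the plan says.** The rules stand in the final paragraph of C2.2 (fMRI Processing/Data Analysis).

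- **Analysis.** The plan says that "change in naming accuracy on the PNT across sessions will be correlated with change in LI", and with RH PTr activation and interhemispheric connectivity. No correlation type, alpha, minimum r, confidence interval or multiplicity rule is given.
- **Hypotheses 1a and 1b.** "A positive correlation between naming gains and" a leftward LI shift (1a) or less RH inhibition of the LH (1b) "will support Hypothesis 1a and 1b, respectively".
- **Hypotheses 2a and 2b.** "A positive correlation between the magnitude of pre-TMS RH PTr activation and" two outcomes is the criterion. The outcome for 2a is "decrease in RH PTr activation across scan sessions"; for 2b it is the leftward LI shift.
- **Hypothesis 3.** The wording changes: "A significant interaction of group and session (analysis C2.1") in favour of Group B is required.

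C2.1 lists the PNT time points as "fixed effects of session (baseline, post-treatment, follow-up"), which makes three. There are four MRI scans. Under C.1, "The first session will conclude with the baseline MRI scan"; further scans follow the first rTMS session, at post-testing and at follow-up. No PNT is listed at the second scan. Planned enrolment (Study timeline) is 6 in Year 1 and 10 in Year 2.

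The p-value thresholds stated in C2.2 apply to activation maps (0.05, cluster FWE) and to selecting regions for the DCM (0.001, uncorrected), not to these correlations.

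**The concern.** Each sentence states what result will count as support, so it works as a decision rule. Taken literally, any r above zero suffices, however small. The paragraph asks for significance for one hypothesis and not for the other four, so it offers no basis for reading significance into those four.

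Two features make this worse. Change across sessions can be computed over several intervals, and the plan does not say which one decides. And for 2a the predictor is part of the outcome, so the predicted sign is expected even if rTMS does nothing.

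The stake is the mechanistic conclusion. Both groups in C 1.2 receive active rTMS and no sham group is described. The claims about laterality, coupling and baseline excitability therefore rest on these correlations, with no untreated contrast to show what noise alone produces.

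**Working it through.** The plan gives no error rate, power or target correlation for these hypotheses, so there is no figure of its own to reproduce.

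**Inputs from the document.** n = 6 + 10 = 16; three PNT administrations, giving 3 pairwise changes, of which 2 start at baseline; four scans, giving 4 × 3 / 2 = 6 pairwise changes, of which 3 start at baseline. Using n = 16 takes both groups together with complete data.

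**Assumptions not in the document.** Normal data; equal variances over time; test-retest correlation w of a measure between sessions, varied from 0 to 0.9.

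**1. Hypotheses 1a and 1b, one interval.** With zero true correlation r is symmetric about 0, so P(r > 0) = 0.50 at any n. Simulation at n = 16 (100,000 data sets) gave 0.499.

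**2. Hypotheses 1a and 1b, interval left open.** With independent session noise, two change scores that share a session correlate ±0.5 in each measure, so the corresponding sample correlations are themselves correlated by about 0.5 × 0.5 = 0.25.
- Either baseline-anchored interval may count: 1 − [1/4 + arcsin(0.25)/(2π)] = 1 − 0.290 = 0.71. Simulation: 0.71.
- Any of three may count: 1 − [1/8 + 3·arcsin(0.25)/(4π)] = 1 − 0.185 = 0.815. Simulation: 0.815, about 82%.

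**3. Hypothesis 2a.** Let B be baseline and L later RH PTr activation, both with variance 1 and correlation w, and no treatment effect. Then Cov(B, B − L) = 1 − w and Var(B − L) = 2(1 − w), so the expected correlation is (1 − w)/√[2(1 − w)] = √[(1 − w)/2], which is above zero for every w below 1.

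| w | Expected correlation | P(r > 0) | P(significant in predicted direction, two-sided 5%) |
|---|---|---|---|
| 0 | 0.71 | 99.9% | 91% |
| 0.5 | 0.50 | 98% | 53% |
| 0.8 | 0.32 | 89% | 22% |
| 0.9 | 0.22 | 81% | 13% |

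**4. Hypothesis 2b.** LI includes right-hemisphere activation, so baseline LI may share signal with baseline RH PTr activation. If the two correlate −0.3 to −0.5 (assumed) and w is 0.5 to 0.8, P(r > 0) with no effect is 64% to 83%. With a two-sided 5% test, false support falls to about 5% to 15%.

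**5. Effect of a significance rule.** The critical value is r = t/√(n − 2 + t²). At n = 16, t = 2.145 on 14 df, so r = 2.145/√(14 + 4.600) = 0.497. False support per hypothesis falls from 50% to 2.5% where the null correlation is truly zero. Power is about 20% for a true r of 0.3, 53% for 0.5, 73% for 0.6 and 90% for 0.7.

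**6. A remedy for 2a.** Correlate B − L with (B + L)/2. Cov = [Var(B) − Var(L)]/2, which is zero when the variances are equal. Simulated false support with the two-sided 5% rule was about 2.5% at w = 0, 0.5, 0.8 and 0.9.

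**The case against.** The strongest reply is that the sentences only state the predicted direction, with ordinary testing taken for granted. Hypothesis 3 has no alpha either, so the plan is sparse on error rates throughout, and these are exploratory correlations in 16 people. In addition, the part of the document between the Preliminary Studies heading and the fMRI design considerations before C.1 was not available to this review, and the available text has no formal statement of the hypotheses. A criterion could stand there. This is fair as to severity: the literal reading is possible but not certain to be the intention. It does not rescue the rule, because nothing in the available text supplies the missing level or interval, and for 2a implied significance would not help.

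A reader might infer three stronger things, none of which the document supports.

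- **That all four hypotheses have a 50% false-support rate, hence 1 − 0.5⁴ = 94% for at least one.** The 50% applies to 1a and 1b at one interval. It is too low for 2a and probably for 2b, and the 94% also needs independence.
- **That the plan lets any interval count, so 82% is its error rate.** The text is silent on this. It could equally mean that all intervals are reported. The 71% and 82% show what the silence permits. They also describe PNT-linked change, not Hypothesis 2, which can draw on four scans.
- **That adding p < 0.05 repairs everything.** It repairs 1a and 1b. It leaves 13% to 91% false support for 2a.

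**Conclusion.** The point holds. As written, C2.2 declares four of five hypotheses supported by the sign of a correlation, over an interval it does not fix. For 1a and 1b that is a coin toss under no relation at one interval, and more if the interval is chosen afterwards. For 2a the rule is close to certain to be met without any rTMS effect unless RH PTr activation is very repeatable between scans; even at an assumed w of 0.9 it is met in about 81% of trials. For 2b the rate is probably above half, but this depends on an assumed link between baseline LI and baseline RH PTr activation.

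The 50% follows from symmetry alone. The 71% and 82% assume independent session noise, and the 2a range assumes equal variances and the stated w. The point should be corrected before the data are analysed. It falls short of a defect that must block the plan, because significance may have been intended and part of the document was not seen.

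**What to change.** Revise the final paragraph of C2.2 as follows.

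1. **Interval.** Name one primary change interval for all four hypotheses. Baseline to post-testing is a natural choice because PNT and MRI are both collected at each end. Label all other intervals secondary.
2. **Hypotheses 1a, 1b and 2b.** State that each is supported only if the correlation is in the predicted direction with two-sided p < 0.05 at the achieved n (r of about 0.50 if all 16 contribute). Name the correlation type and report r with its 95% CI. Say whether p-values are adjusted for multiplicity: four independent tests at 2.5% each give 1 − 0.975⁴ = 9.6% for at least one false support.
3. **Hypothesis 2a.** Replace the baseline-versus-change correlation with a method that allows for regression to the mean, for example correlating the change with the average of the baseline and later values. Note that this relies on similar variances at the two scans.
4. **Hypothesis 2b.** Report the correlation between baseline LI and baseline RH PTr activation, and interpret 2b in its light.
5. **Consistency.** Make any criterion stated elsewhere with the hypotheses match this paragraph.

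The cost is a few sentences and no new data. The downside is that fewer hypotheses will be declared supported: at n = 16 a true r of 0.5 would be detected only about 53% of the time. The confidence intervals will show that limit openly.

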For the majority of individuals, language is supported by a strongly left- lateralized network of brain regions. When a left hemisphere (LH) stroke injures any of the brain regions involved in this network, other regions are recruited in a compensatory fashion via functional cortical reorganization. There is considerable evidence that compensatory recruitment of undamaged left hemisphere perilesional brain regions results in more optimal recovery of language functions than does recruitment of regions in the right hemisphere (RH) [11-14, and many others]. Furthermore, recruitment of LH perilesional regions, specifically left frontal regions, predicts treatment-related increases in correct naming for individuals with chronic aphasia [15-16].

One account for the poorer outcomes related to RH contralesional recruitment has been framed in terms of interhemispheric inhibition. In its undamaged homeostatic state, the LH language network actively inhibits the RH during language-related tasks via transcallosal projections [17]. This is thought to be an adaptation due to LH specialization, and hence optimization, for language tasks, particularly language production. According to this account, when the LH network is damaged as a result of a stroke, the RH is released from this inhibition, allowing it to be recruited during language production tasks. The now overactive RH in return inhibits the preserved perilesional cortical areas in the LH, preventing them from being recruited [18-19]. As the RH is less specialized for language, this hemispheric shift in activation may result in improved language abilities during recovery, albeit improvements that are relatively suboptimal compared to those that result from more efficacious LH perilesional recruitment [13].

A2. Application of non-invasive brain stimulation to optimize cortical reorganization

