A case study published by Turkeltaub and colleagues [27] evaluated the immediate neurobiological effects of inhibitory rTMS. The single participant performed an overt naming task (identical to the one used by Martin et al [30] discussed above) while undergoing an fMRI scan immediately prior to and following the first rTMS session in a series. The rTMS immediately reduced activity at the site of stimulation (RH PTr), but no corresponding LH laterality shift was observed. Furthermore, a subsequent RH stroke further worsened the participant's aphasia symptoms, suggesting that some RH areas exclusive of RH PTr were involved in the initial rTMS induced recovery. However, this evidence is indirect and does not preclude both RH and LH recruitment, nor does it suggest that RH recruitment is *as efficient* as LH recruitment.

Finally, no studies to date have directly tested the claims of the inhibition hypothesis regarding the effect of rTMS on directional inhibitory influences between the RH and LH. To evaluate these claims it is important to measure not only activity changes but also *interactivity* changes to see how the *system* is changing as a result of rTMS across time. Furthermore, as no study has yet collected functional neuroimaging measures throughout the rTMS time course, it is impossible to infer how the acute effects of rTMS relate to the cumulative effects of multiple rTMS sessions, or longer-term changes that occur weeks and months after the conclusion of rTMS.

In summary, inhibitory rTMS targeting RH PTr appears to be a promising approach to treating language difficulties, particularly naming deficits, in chronic aphasia. However, before regular clinical use of rTMS can be considered, we need to have a better understanding of both the *potential sources of response variability*, and the *neurobiological mechanisms* underlying the beneficial effects of rTMS.

B. Preliminary Studies

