The second visit will begin with the first rTMS session (also described below) which will then be followed directly by the post-rTMS MRI scan. Starting the following day, the subsequent nine sessions will consist only of rTMS for a total of 10 rTMS sessions. The sessions in the rTMS series will take place daily across two weeks excluding weekends. A post-testing session, scheduled the week after the final rTMS session, will include an MRI scan and repeat administration of the language assessments that were administered during the screening visit. A final follow-up session, identical in design to the post-testing session, will be scheduled in an additional 7-10 weeks. All study-related evaluations will be administered by the PI (a licensed speech-language pathologist) or in Year 2 by the staff speech-language pathologist. Study participants will receive up to \$275 for time and local travel expenses and up to an additional \$1500 to defray lodging expenses incurred as part of study participation, to be pro-rated if they do not complete all study procedures (including follow-up visits).

Participants will be pseudo-randomly assigned to an rTMS treatment group (priming stimulation vs no priming stimulation) depending on the outcome of their baseline fMRI (described in C1.1, below). That is, an equal number of participants with and without baseline RH PTr activation will be approximated in each group.

C.1.1 MRI Procedure

fMRI Overt Confrontation Picture Naming Task. Images will be acquired using a 3.0 Tesla parallel-acquisition, echo-planar equipped Siemens MRI scanner. Participants will lay supine in the scanner wearing hearing protection and over-ear headphones. Their heads will be secured with foam padding to minimize movement.

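### The rule for Hypothesis 1b is a change-score correlation with no condition on the sign of baseline RH-to-LH coupling, so it cannot separate release from inhibition from growing excitation

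*Combined protocol and SAP*

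**What the plan says.** The dynamic causal modeling (DCM) text in section C2.2 selects an effective-connectivity model from "all possible combinations of bi-directional connections between the regions". It states no constraint on the sign of any connection. The weights are then reduced to one figure per scan: "Coupling weights for interhemispheric connections will be summed for each participant for each scanning session". Change in naming accuracy on the Philadelphia Naming Test (PNT) is correlated with change in "interhemispheric effective connectivity across sessions", and a positive correlation of naming gains with "a decrease in RH inhibition of LH (more positive RH to LH directional coupling weights") is taken as support for Hypothesis 1b.

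The mechanism behind the hypothesis is in section A1: "The now overactive RH in return inhibits the preserved perilesional cortical areas in the LH, preventing them from being recruited". Section A.3.2 gives the reason for testing it, namely that "no studies to date have directly tested the claims of the inhibition hypothesis regarding the effect of rTMS on directional inhibitory influences".

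Section C2.2 also allows further exploratory DCM analyses, but it makes them optional and names no check of sign.

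**The concern.** For an absolute coupling strength, a negative weight means inhibition and a positive weight means excitation. A move from negative toward zero is less inhibition. A move upward from zero or above is more excitation. The rule for 1b uses only the direction of change and describes both moves as reduced inhibition.

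The account in section A1 has RH inhibition of the LH as its premise, so there must be inhibition at baseline for rTMS to relieve. No step in C2.2 looks at whether there is. A positive correlation could then be reported as release from inhibition when the data show the RH increasingly driving the LH. That is a different explanation of recovery. Section A.3.2 itself discusses a case in which RH areas other than the stimulated one seemed to contribute to the rTMS-related recovery. Since the study is presented as the first direct test of the directional claim, the test should be able to tell the two explanations apart.

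**Working it through.** The plan gives no coupling weights, expected correlation, alpha or power for Hypothesis 1b, so there is no planned figure to reproduce. The check is of the rule's logic. The sample size is 6 + 10 = 16 (Study timeline). All weights below are assumed for illustration.

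**Step 1: the change score drops the baseline.** For participant i the predictor is D_i = post_i − pre_i, and the statistic is corr(naming gain_i, D_i). If post_i = pre_i + d_i, then D_i = d_i whatever pre_i is. For example:

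| Pre | Post | Change | What happened |
|---|---|---|---|
| −0.50 | −0.30 | +0.20 | less inhibition |
| 0 | +0.20 | +0.20 | excitation appears |
| +0.10 | +0.30 | +0.20 | more excitation |

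**Step 2: the same with 16 simulated participants.** One set of changes and naming gains was held fixed and only the baselines were varied.

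| Assumed baseline weights | Inhibitory at baseline | r | p |
|---|---|---|---|
| −0.6 to −0.4 | 16 of 16 | 0.3011 | 0.257 |
| all zero | 0 of 16 | 0.3011 | 0.257 |
| +0.1 to +0.3 | 0 of 16 | 0.3011 | 0.257 |

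The value of r is not a forecast. What matters is that it is the same in all three rows, as Step 1 requires.

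**Step 3: summing signed weights.** Take two RH-to-LH connections, one inhibitory and unchanged at −0.20, the other excitatory and rising from +0.10 to +0.40.
- Sum before: −0.20 + 0.10 = −0.10
- Sum after: −0.20 + 0.40 = +0.20
- Change in sum: +0.20 − (−0.10) = +0.30
- Change in the inhibitory connection: 0

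The baseline sum here is negative, so a check on the sum alone would pass. Only the weights per connection show that inhibition did not change.

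**Step 4: which baseline check is valid.** A tempting index is the sum of the negative weights only, tested against zero. That index is at or below zero by construction. With 16 participants, 2 connections, an assumed estimation noise SD of 0.2 and a one-sided alpha of 0.05, simulation gave these rates of finding inhibition at baseline:

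| True weights | Negative-only sum | Plain signed sum |
|---|---|---|
| all 0 | over 99% | about 5% |
| all +0.1 | 97% | about 0% |

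The negative-only index reports inhibition where none exists. The plain signed weight does not.

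**Step 5: precision of the valid check.** A one-sided 5% t test with 16 participants has 15 degrees of freedom and critical t = 1.753. The baseline mean must lie at least 1.753/√16 = 0.438 between-participant SDs below zero to be declared negative.

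**The case against.** **Support needs a correlation across participants.** This stands. A reader might infer that each participant whose weight rises is classified as released from inhibition. Section C2.2 does not say that; it classifies nobody. The difficulty is with the label given to the correlated variable.

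**Zero may not be the boundary.** Section C2.2 does not say whether the summed weights are absolute couplings or task-dependent changes in coupling, and the methodological considerations before C.1 describe the coupling as activity-dependent. If they are task-dependent changes alone, a positive value does not show absence of inhibition. This also stands. It means that the plan must say which quantity is used before any sign can be read.

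**The hypothesis may be worded more fully elsewhere.** The text available here does not contain the full statement of Hypothesis 1b, so it may claim only a relative shift. The decision rule in C2.2 is nevertheless complete as it stands, uses the word inhibition, and carries no sign condition.

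**The sign is not lost.** Weights exist for each participant and scan, so the baseline can be inspected. That makes the repair cheap, but the plan does not commit to doing it or to letting it affect the conclusion. The companion results on laterality and RH PTr activation do not carry the sign of the coupling.

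**Nothing shows that non-inhibitory baselines are likely.** This is fair. Section C.1 plans that "an equal number of participants with and without baseline RH PTr activation will be approximated in each group", and section A.3.1 expects little RH PTr recruitment in people without left frontal lesions. Those statements make uneven baselines plausible, but they concern activation and not the sign of coupling.

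**Conclusion.** The point holds as a flaw in the decision rule. As written, a positive correlation can be declared support for release from inhibition with no inhibitory RH-to-LH influence in any participant, because the statistic is identical for negative, zero and positive baselines. Summing signed weights allows the same misreading even when the baseline sum is negative.

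The first part is algebra and depends on no assumed value. Reading the sign as inhibition or excitation assumes that the weights are absolute couplings. The size of the practical effect cannot be given, because the documents report no weights.

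A reader might go further and infer that 1b will be falsely supported, or that baseline coupling is probably excitatory. The documents support neither. Nor does the point reach the PNT naming analysis or Hypotheses 1a, 2a, 2b and 3, whose rules do not use coupling weights. The change is worth making because the rule can lead to a wrong mechanistic conclusion and the remedy uses estimates already planned.

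**What to change.** In section C2.2:

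1. State that the weights used for Hypothesis 1b are absolute RH-to-LH coupling strengths during naming, and not task-dependent changes alone.
2. Report signed baseline and post-rTMS RH-to-LH weights for each participant, and for each connection where available, so that a case like Step 3 can be seen.
3. Test whether the plain signed baseline RH-to-LH weight is below zero. Do not use a sum restricted to negative weights for this test.
4. Keep the planned correlation in all participants. Call a positive correlation support for release from inhibition only if baseline RH-to-LH coupling is net negative. Otherwise report it as increased RH-to-LH excitation.

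This needs no new scans or participants, only a few lines of post-processing. Keeping everyone in the correlation avoids the loss from restricting it to participants with negative baselines: at an assumed two-sided 0.05, the critical |r| is 0.497 with 16 participants but 0.707 with 8. The costs are that Hypothesis 1b may be declared supported less often, and that the baseline sign test is imprecise with 16 participants, so a modest true inhibition could go undetected. A baseline result that is not clearly negative should therefore be shown with its confidence interval.
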